1.2.3.1 Study CC-90009-AML-001

Enrollment of subjects in Part A Dose Escalation of the study has been completed and a total of 72 subjects were treated. (One subject, in the 3.6 mg with dexamethasone premedication cohort, was reenrolled under a new subject number after discontinuing from study and subsequently relapsing after 8 months of complete remission. The subject's two subject numbers were consolidated, and they were counted only once.) All treated subjects had R/R AML. To date, 4

dosing schedules of CC-90009 have been explored; once daily dosing on Days 1-5 of a 28-day cycle (0.3 mg to 4.5 mg), Days 1-7 of a 28-day cycle (3.6 mg), Days 1-10 of a 28-day cycle (3.0 mg), and Days 1-3 and 8-10 of a 28-day schedule (3.0 and 3.6 mg). Dose levels of 3.6 mg and above and the 3.0 mg dose level on the Days 1-10 schedule included premedication with dexamethasone for subjects enrolling starting with Protocol Amendment 5. As of 01 Apr 2021, enrollment in Part A of the study has been completed. After a review of Part A data, the SRC recommended that CC-90009 be dosed at 3.6 mg on Days 1–5 with dexamethasone premedication in Part B Dose Expansion in both R/R AML and R/R HR-MDS. After review of initial data from Part B Dose Expansion with an observation of a higher rate of sepsis in the Part B R/R AML cohort as compared to R/R AML cohorts in Part A, the SRC recommended to close R/R AML and R/R HR-MDS cohorts receiving CC-90009 at 3.6 mg Days 1–5 for enrollment, and two new dose levels (2.4 mg and 3.0 mg on Days 1-7) were recommended to be expanded as part of a dose optimization and sepsis mitigation strategy.

As of the 13 Aug 2021 cutoff date, preliminary data are available for 80 subjects with R/R AML and 2 subjects with R/R HR-MDS. Of the 82 subjects treated with CC-90009, 79 (96.3%) had discontinued from treatment and out of these, 76 (92.7%) had discontinued from the study. The most common reason for treatment discontinuation was progressive disease in 24 (29.3%) subjects. The most common reason for study discontinuation was death in 67 (81.7%) subjects.

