In Part B, subjects with R/R AML who are eligible include subjects who relapsed after allogeneic HSCT, who are in second or later relapse, who are refractory to initial induction or re-induction treatment, who are refractory to or relapsed after hypomethylating agents (HMA failure defined as primary progression or lack of clinical benefit after a minimum of 6 cycles or unable to tolerate HMA due to toxicity), or who relapsed within 1 year of initial treatment (excluding those with favorable-risk status; see Appendix H).

In Part B, subjects with R/R HR-MDS who are eligible include subjects who scored > 3.5 points in the Revised International Prognostic Scoring System (IPSS-R) [eg, IPSS-R intermediate risk (in combination with more than 10% bone marrow blasts or poor or very poor IPSS-R cytogenetic risk), IPSS-R high and IPSS-R very high risk] and are not suitable for other established therapies (eg, transplant or hypomethylating agent) (Appendix G).

[figure not shown]
Note that the 3.6 mg dose of CC-90009 on Days 1-5 schedule with dexamethasone premedication had been selected as the Part B dose and schedule in both R/R AML and R/R HR-MDS for the dose expansion part of the study (Part B). Due to a high rate of sepsis (75%) observed in the initial 8 R/R AML subjects enrolled in Part B at dose level 3.6 mg Days 1-5 with dexamethasone premedication, the SRC recommended to close R/R AML and R/R HR-MDS cohorts receiving CC-90009 at 3.6 mg Days 1-5 for enrollment.

New cohorts in Part B will be enrolled at CC-90009 dose levels of 2.4 mg Days 1-7 and 3.0 mg Days 1-7. The selection of these doses at the Days 1-7 schedule is based primarily on PK and PD analysis and safety and tolerability data. These R/R AML and R/R HR-MDS subjects will be

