6 PROCEDURES

Any questions regarding the protocol should be directed to the Celgene Medical Monitor or designee. The procedures conducted for each subject enrolled in the study are outlined in Table 4 and Table 5 for Part A and Table 6 and Table 7 for Part B. All study visits will have $a \pm 2$ day window unless otherwise specified below or in the Table of Events. All laboratory blood samples should be drawn predose unless otherwise specified (eg, PK samples). For subjects enrolled on an alternate schedule (eg, D1-3/D8-10, D1-7, or D1-10 dosing schedules), please refer to Table of Events in Appendix K and Appendices M-O.

The study procedures should be recorded in the source document and the electronic case report forms (eCRF). In the event subjects fail Screening, minimal information will be documented on the eCRFs, per database instructions.

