7.2 Treatment Administration and Schedule

CC-90009 will be administered QD on Days 1 to 5 (on the D1-5 dosing schedule) of Cycles 1 to 4. Subjects will be closely monitored throughout the administration of CC-90009 and for 1 hour following each administration. In addition, subjects will be admitted as inpatients for each administration of CC-90009 and monitoring in Cycle 1. For Cycles ≥ 2 , subjects will either be admitted as inpatients or treated/monitored in a LSU per Investigator's discretion. Subjects with

Grade ≥ 2 hypocalcemia in any cycle should be treated as inpatients in subsequent cycles (an exception can be made for subjects with grade 2 hypocalcemia lasting less than 24 hours that recovers without IV calcium [eg, calcium gluconate or calcium chloride] after discussion with the Celgene medical monitor). The SRC may evaluate modified dosing schedules (eg, increasing from 5 to up to 10 consecutive days of dosing, intermittent schedules or longer infusion times) in additional cohorts, if necessary, based on toxicity, PK profiles, and PD findings.

For CC-90009 doses at or above 3.6 mg, all subjects will receive a dose of steroids (eg, dexamethasone 10 mg IV (or by mouth [PO] or equivalent) 30 min to 3 hrs prior to each daily dose of CC-90009 (Table 4 –Table 7, Appendix K, or Appendices M-O). For CC-90009 dosed at 3.0 mg on the Days 1-7 and Days 1-10 dosing schedules, steroid premedication is recommended for each of the dosing days. On these schedules with longer dosing days, a lower dose of dexamethasone may be given (minimum of 4 mg) per Investigator's judgement based on the subject's expected tolerability of corticosteroids. The frequency and/or the dose of dexamethasone (or equivalent) administration may be modified based on evaluation and recommendation by the SRC (eg, D1-5, D1-7, D1-10, or D1, D3, D5).

All subjects will be required to start calcium, calcitriol, and vitamin D supplementation at least 3 days prior to the first dose of CC-90009 in each cycle and continue until \geq 3 days after the last dose of CC-90009 in each cycle (eg, \geq Day 8 when CC-90009 is administered on Days 1-5, \geq Day 10 when CC-90009 is administered on Days 1-7, or \geq Day 13 when CC-90009 is administered on Days 1-3/8-10 or Days 1-10). Supplementation may be extended if hypocalcemia occurs (refer to Section 7.2.13.2). The time and date of administration will be recorded on a diary card.

The calcium/calcitriol/vitamin D supplementation regimen is:

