7.2.14 Definition of Overdose

Overdose, as defined for this protocol, refers to CC-90009 dosing only. On a per dose basis, an overdose is defined as the following amount over the protocol-specified dose of CC-90009 assigned to a given subject, regardless of any associated adverse events or sequelae:

• 10% over the protocol-specified dose

On a schedule or frequency basis, an overdose is defined as anything more frequent than the protocol required schedule or frequency.

Complete data about drug administration, including any overdose, regardless of whether the overdose was accidental or intentional, should be reported in the case report form. Refer to Section 10 for the reporting of adverse events associated with overdose.

7.2.15 Dosage Modifications for Concomitant Use of Strong CYP3A4 Inhibitors in Part B Dose Expansion

In Part B, dosage modification of CC-90009 based on concomitant use with a strong CYP3A4 inhibitor (See Section 8.2 for list of example CYP3A4 inhibitors) will be as follows:

- For 3.0 mg Days 1-7 cohort, reduce CC-90009 dose to 2.0 mg
- For 2.4 mg Days 1-7 cohort, reduce CC-90009 dose to 1.5 mg

Resume the CC-90009 dosage that was used prior to concomitant use of a strong CYP3A4 inhibitor 3 days after discontinuation of the inhibitor.

No dose modification is required for concomitant use of moderate CYP3A4 inhibitors.

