8.3 Required Concomitant Medications and Procedures

All subjects will be required to start calcium, calcitriol, and vitamin D supplementation at least 3 days prior to the first dose of CC-90009 in each cycle and continue until \geq 3 days after the last dose of CC-90009 in each cycle. Supplementation may be extended if hypocalcemia occurs (refer to Section 7.2.13.2). Subjects will document (date and time) taking the supplements on diary cards that will be reviewed on Day 1 of each cycle and at the EOT visit.

The calcium/calcitriol/vitamin D supplementation regimen is:

- Calcium carbonate 500 mg elemental calcium PO 3 TID (taken after meals to increase absorption)
 - Alternative preparations of calcium can be substituted but they must equal at least 1200 mg of elemental calcium per day given in divided doses (eg, TID).
 - If the subject is on a proton pump inhibitor (PPI) or has gastric achlorhydria, then administer calcium citrate 630 mg elemental calcium PO TID or closest higher dose based on available strengths.
- Calcitriol 0.25 micrograms PO QD
- Vitamin D supplementation is based on the Screening serum 25-hydroxyvitamin D level:
 - Level < 12 ng/mL excluded from the study
 - Level 12 20 ng/mL Vitamin D3 or D2 50,000 IU weekly
 - Level > 20 ng/mL- Vitamin D3 or D2 1000 IU QD

The risk of TLS with CC-90009 is unknown. Subjects should be adequately hydrated (eg, 2 to 3 liters of oral or IV fluids per day) starting the day prior to CC-90009 administration and continuing through each day of CC-90009 administration.

Subjects given CC-90009 at daily doses \geq 3.6 mg will be administered concurrent dexamethasone per Section 7.2. Subjects enrolled on other dose levels may be administered corticosteroid premedication as per SRC recommendation (eg, at the 3.0 mg dose level on the Days 1-7 and Days 1-10 schedules).

Routine infectious disease prophylaxis including appropriate prophylactic antibiotic, antiviral, anti-pneumocystis, antifungal, or other prophylaxis should be implemented during the study according to institutional standard medical practice.

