Appendix N: Part B Table of Events for D1-7 Dosing Schedule

Table 35:Table of Events for Part B (D1-7 Schedule) of Cycle 1

						Ті	reatment Pe	riod				
	Screening						Cycle 1					
					WK1				WK2	WK3	W	'K4
Events ^a	D-28 to -1	D1	D2	D3	D4	D5	D6	D7	D8	D15	D22	D28 ^c
Study Entry (Section 6.1)												
Informed consent	Х											
Inclusion/ exclusion criteria	Х											
Medical ^{t/} oncologic history	Х											
AML or MDS Disease Assessment and Cohort Assignment ^b	Х											
Demographics	Х											
IRT registration	Х	Х										
Pregnancy risk counseling and contraceptive compliance confirmation	Х				As specifi	ed in Sectio	on 6.1.1 and	the PPP in	Appendix L	_		
Prior/ concomitant medications & procedures (Section 6.2.1)	Х	Х	Х	Х	Х	Х	Х	Х	Х	Х	Х	
CC-90009 Administration (Section	n 7)											
Calcium, calcitriol, and vitamin D supplements and recording on diary card (refer to Section 7.2)	X (D-3 to D-1)	Х	x	х	X	х	х	х	X ^d			
Provide/review diary card	Х	Х										
Corticosteroid administration (dexamethasone) (refer to Section 7.2) for doses 3.6 mg and above		Х	Х	Х	х	Х	х	Х				
IV administration of CC-90009		Х	Х	Х	X	X	Х	Х				

Table 35:Table of Events for Part B (D1-7 Schedule) of Cycle 1

						Ті	eatment Pe	riod				
	Screening						Cycle 1					
					WK1				WK2	WK3	W	K4
Events ^a	D-28 to -1	D1	D2	D3	D4	D5	D6	D7	D8	D15	D22	D28c
Monitoring as an inpatient		Х	Х	Х	X	Х	Х	Х				
Safety Assessments (Section 6)												
Adverse Event Evaluation (Section 6.2.2)	X	Х	Х	Х	Х	Х	Х	X	X	Х	Х	
Height	X											
Weight (Section 6.2.3)	X	Х							Х	Х	Х	
Vital Signs (Section 6.2.3)	Х	Xf	Xf	Xf	Xf	Xf	Xf	Xf	Х	Х	Х	
Physical Examination (Section 6.2.4)	X	Х							X			
ECOG PS (Appendix D)	Х	Х							Х			
SARS-CoV-2 Viral Testing ^r	X (within 7 days of D1)											
12-lead ECG (in triplicate, Section 6.2.5)	X (≥72 hrs prior to D1)	Xf						Xf	X			
Adverse Event Evaluation (Section 6.2.2)	Х	Х	Х	х	х	Х	Х	Х	X	Х	Х	
Height	Х											
Weight (Section 6.2.3)	Х	Х							Х	Х	Х	
Vital Signs (Section 6.2.3)	Х	Xf	Xf	Xf	Xf	Xf	Xf	Xf	Х	Х	Х	
Physical Examination (Section 6.2.4)	X	Х							X			
Safety Assessments (Section 6)				•								·
ECOG PS (Appendix D)	Х	Х							Х			

Table 35:Table of Events for Part B (D1-7 Schedule) of Cycle 1

						Tr	reatment Pe	riod				
	Screening						Cycle 1					
					WK1				WK2	WK3	W	/K4
Events ^a	D-28 to -1	D1	D2	D3	D4	D5	D6	D7	D8	D15	D22	D28 ^c

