Appendix O: Part A Table of Events for D1-10 Dosing Schedule

Table 37:Table of Events for Part A (D1-10 Schedule) of Cycle 1

								Trea	tment Pe	riod						
	Screening								Cycle 1							
					WK1					WK2		WK3	W	K4	WK5 ^b	WK6 ^b
Events ^a	D-28 to -1	D1	D2	D3	D4	D5	D6	D7	D8	D9	D10	D15	D22	D28c	D29	D36
Study Entry (Section 6.1)																
Informed consent	Х															
Inclusion/ exclusion criteria	Х															
Medical/ oncologic history	X															
Demographics	Х															
IRT registration	X	Х														
Pregnancy risk counseling and contraceptive compliance confirmation	X					As spo	ecified in	Section	6.1.1 and	the PPP	in Appen	ıdix L				
Prior/ concomitant medications & procedures (Section 6.2.1)	Х	Х	X	Х	Х	Х	Х	Х	Х	X	X	Х	Х		Х	X
CC-90009 Administration (Sect	tion 7)															
Calcium, calcitriol, and vitamin D supplements and recording on diary card (refer to Section 7.2)	X (D-3 to D-1)	Х	Х	Х	Х	X	Х	Х	Х	Х	X ^d			X ^d		X ^d
Provide/ review diary card	Х	Х														
Corticosteroid administration (dexamethasone) (refer to Section 7.2) for doses 3.0 mg and above		X	x	X	x	х	X	Х	X	Х	x					
IV administration of CC-90009 ^e		Х	Х	Х	Х	X	Х	Х	X	Х	Х					
Monitoring as inpatient		Х	Х	Х	Х	Х	Х	Х	Х	Х	Х					
Safety Assessments (Section 6)																
Adverse Event Evaluation (Section 6.2.2)	Х	Х	X	Х	X	Х	Х	Х	Х	Х	X	Х	х		Х	X
Height	Х															

CC-90009-AML-001 Amendment 9 Final: 31 Mar 2022

Table 37:Table of Events for Part A (D1-10 Schedule) of Cycle 1

								Treat	tment Pe	riod						
	Screening								Cycle 1			r	1		1	
					WK1	[r			WK2	T	WK3	W	K4	WK5 ^b	WK6 ^b
Events ^a	D-28 to -1	D1	D2	D3	D4	D5	D6	D7	D8	D9	D10	D15	D22	D28 ^c	D29	D36
Weight (Section 6.2.3)	Х	Х							Х			Х	Х			
Vital Signs (Section 6.2.3)	Х	\mathbf{X}^{f}	Xf	\mathbf{X}^{f}	Xf	Xf	\mathbf{X}^{f}	\mathbf{X}^{f}	\mathbf{X}^{f}	\mathbf{X}^{f}	\mathbf{X}^{f}	Х	Х		Х	Х
Physical Examination (Section 6.2.4)	X	Х							Х							
ECOG PS (Appendix D)	Х	Х							Х							
12-lead ECG (in triplicate, Section 6.2.5)	X (≥72 hrs prior to D1)	\mathbf{X}^{f}							Х		Xf					
LVEF (ECHO/MUGA scan; Section 6.2.6)	X															
Pregnancy testing per PPP (FCBP only; Section 6.2.7)	Xg								Х			Х	X			Х
Hematology laboratory tests (Section 6.2.8)	X (D-14 to -1)	Х	Х	Х	Х	Х	Х	Х	Х	Х	X	Х	X		X	Х
G6PD (Section 6.2.8)	Х															
Serum chemistry laboratory tests (Section 6.2.8) ^h	X (D-3 to -1)	\mathbf{X}^{i}	X ⁱ	X ⁱ	X	X	Х	Х	Х	Х	Х	Х	х		Х	Х

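### The dexamethasone row in the Part B Days 1-7 schedules (Tables 35 and 36) is limited to 3.6 mg and above, which no assigned dose reaches, while Section 7.2 recommends premedication at 3.0 mg

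*Combined protocol and SAP*

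**What the plan says.** Appendix N holds the schedules for Part B Days 1-7: Table 35 for Cycle 1 and Table 36 for later cycles. Both contain a row reading "Corticosteroid administration (dexamethasone) (refer to Section 7.2) for doses 3.6 mg and above", ticked on Days 1 to 7. Section 6 directs sites with subjects on an alternate schedule, Days 1-7 included, to these appendices: "please refer to Table of Events in Appendix K and Appendices M-O".

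Section 3.1 sets the doses: "New cohorts in Part B will be enrolled at CC-90009 dose levels of 2.4 mg Days 1-7", with 3.0 mg Days 1-7 as the second level. Section 4.1 names the same two cohorts. Section 7.2.15 lowers both doses when a strong CYP3A4 inhibitor is used ("For 3.0 mg Days 1-7 cohort, reduce CC-90009 dose to 2.0 mg", and 2.4 mg goes to 1.5 mg).

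Section 7.2 has two tiers. At 3.6 mg or more, every subject is to receive a steroid. At 3.0 mg on Days 1-7 or Days 1-10, "steroid premedication is recommended for each of the dosing days". Section 8.3 is softer about doses below 3.6 mg: "Subjects enrolled on other dose levels may be administered corticosteroid premedication as per SRC recommendation", with 3.0 mg on these two schedules as its example. Section 1.2.4 says the same.

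The Days 1-10 schedules (Appendix O, Tables 37 and 38) word the row differently: "Corticosteroid administration (dexamethasone) (refer to Section 7.2) for doses 3.0 mg and above".

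**The concern.** A schedule of events is what site staff work from day to day. Here it ticks a premedication on seven days and then attaches a dose condition that excludes every subject on the schedule. The cohort for which the body of the protocol recommends the premedication is excluded with the rest.

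Section 3.1 says steroids were introduced to reduce the risk of hypotension. Under Table 12, hypotension needing vasopressors is Grade 3, and Section 7.2.6 does not list hypotension among the exceptions to the dose-limiting toxicity definition. The 3.0 mg cohort opens with a safety run-in of up to 6 subjects, judged on the Part A criterion of 2 or more subjects with dose-limiting toxicity (Sections 3.1 and 7.2.8). If some sites followed the row label and others followed Section 7.2, premedication could differ between subjects in that very small tolerability assessment.

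**Working it through.** The plan gives no figure to reproduce. The check compares the row's threshold with every dose the plan names for this schedule.

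| Daily dose, Part B Days 1-7 | Source | Reaches 3.6 mg? | Named in the Section 7.2 recommendation? |
|---|---|---|---|
| 3.0 mg | Sections 3.1, 4.1 | No (0.6 mg short) | Yes |
| 2.4 mg | Sections 3.1, 4.1 | No (1.2 mg short) | No |
| 2.0 mg | Section 7.2.15 | No (1.6 mg short) | No |
| 1.5 mg | Section 7.2.15 | No (2.1 mg short) | No |

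The row's threshold is met by 0 of 4 doses. The Section 7.2 recommendation names 1 of 4.

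Four readings that might rescue the label were then tested.

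1. *Could a subject move up to 3.6 mg on Days 1-7?* Section 7.2.9 allows escalation in later cycles, with Safety Review Committee (SRC) approval, to a dose found tolerable in a higher cohort, and footnote k of Table 36 mentions intra-subject escalation. Section 7.2.11, however, bars Part B escalation beyond the MTD. Part A ran "Days 1-7 of a 28-day cycle (3.6 mg" and no other dose on that schedule (Section 1.2.3.1). Section 1.3.4 says this regimen was not well tolerated. It also says that an NTD was found on three of the four schedules, all except Days 1-3/8-10. By inference 3.6 mg Days 1-7 is the NTD, so this route is closed in practice. Toxicity reductions only go lower.
2. *Does the row serve the earlier 3.6 mg Part B cohorts?* No. Those were Days 1-5, use Tables 6 and 7, and are closed to enrollment.
3. *Do the schedules print only the mandatory threshold?* Not consistently. Tables 37 and 38 print 3.0 mg for Days 1-10, where premedication at 3.0 mg is also only recommended. Section 7.2 gives that recommendation for both schedules in a single sentence. One schedule's tables follow it and the other's do not.
4. *Is the threshold right somewhere?* Yes. It suits the Part A Days 1-7 tables, because that schedule was run at 3.6 mg. A carry-over from Part A would explain the label, but the documents do not say so.

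**The case against.** The strongest defence is that the protocol already handles this. The row cites Section 7.2, which names 3.0 mg Days 1-7 outright, and Sections 1.2.4 and 8.3 name it again. A site would have to ignore the row's own reference to miss the recommendation. This stands, and it limits the consequence.

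A second defence is that 3.6 mg is the mandatory threshold, and exclusion criterion 21 (Section 4.3) uses it too, so the row may be meant to show required administration only. This stands in part: no two binding rules conflict. But on that reading the row is empty for both cohorts, and Tables 37 and 38 do not follow the same convention.

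Third, protection against hypotension does not rest on this row alone. Cycle 1 dosing is inpatient, vital signs are taken before and after each dose (Section 6.2.3), and Section 7.2.13.8 sets out management. This also stands.

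A reader might infer more: that the plan withholds required prophylaxis, or that the run-in's toxicity assessment is compromised. The documents do not support either. Section 7.2 recommends premedication at 3.0 mg without requiring it, and it lets the investigator lower the dexamethasone dose and the SRC change dose or frequency. Section 1.3.4 records 3.0 mg Days 1-5 without dexamethasone as an MTD. That gives only partial reassurance, because 3.0 mg Days 1-7 was not tested in Part A. Nor is there a gap at 2.4 mg, where Section 7.2 makes no recommendation.

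**Conclusion.** The point holds as a minor inconsistency that is wrong as written. The dexamethasone row in Tables 35 and 36 carries a threshold that none of the four named Part B Days 1-7 doses reaches, and it disagrees with the Section 7.2 recommendation for the 3.0 mg cohort. The mismatch concerns that cohort only. It is worth correcting because it is a dose condition on a safety premedication in the schedule that sites are told to use.

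The conclusion rests on assigned doses and on the inference that 3.6 mg Days 1-7 is not available by escalation. It does not rest on any estimate of harm: the documents give no rate of hypotension or dose-limiting toxicity at 3.0 mg Days 1-7 with or without steroid. No endpoint, analysis population or decision rule changes.

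**What to change.** In Tables 35 and 36, replace the dose phrase in the dexamethasone row with: 'recommended at 3.0 mg; see Section 7.2 for dose, frequency and SRC modifications'.

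Keep it to a pointer. Printing the 4 mg minimum in the row would be a mistake: in Section 7.2 that is the floor for a lower dose given at the investigator's judgement, beside an example dose of 10 mg, and on its own it could be read as the dose to give. A separate rule for 2.4 mg is also best left out, since Sections 1.2.4 and 8.3 give 3.0 mg Days 1-7 itself as an example of a level premedicated on SRC recommendation.

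In the same edit, check exclusion criterion 21, which excludes subjects unable to take corticosteroids only at 3.6 mg or above. It may need no change, because premedication at 3.0 mg is not required, but the decision should be deliberate.

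The cost is one row label in each of two tables plus that check. Relabelling leaves study procedures, data collection and analysis as they are.
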